#### **Table 4 study plan**

Addition in footnote (e): For subjects withdrawn from treatment but who had not progressed at the time of AZD9291 discontinuation. **Follow up to be performed every 6 weeks (± 1 week) relative to the date of enrolment until end of study (including survival follow-up period).**

Addition of footnote (g) **Survival status to be performed every 6 weeks (± 1 week) relative to the date of enrolment until end of study**

**Section 4.1** modified

**In 3)** Laboratory results for T790M meeting still needs to be available at the site but is not faxed anymore with the enrolment form. This is in order to avoid confidentiality issue.

Addition of: **Consenting patients who do not fulfil the eligibility criteria must not be enrolled (dosed) into the study and will be discontinued. They will be considered screening failures and only demography data, reason for discontinuation will be recorded. Supporting safety information can be collected in case of SAE, if applicable.**

**Section 4.2** modified

**In 3)** Removal of the restriction on CYP3A4 inhibitors as Study 12 has shown that CYP3A4 inhibitors have no effect on AZD9291.

**Section 4.3** modified

Addition of **QTc interval prolongation with signs/symptoms of serious arrhythmia** as a criteria for discontinuation to be aligned with AstraZeneca Project Specific Safety

## Requirements.

### Section 4.3.1 modified

**Addition: Patients may continue study treatment beyond disease progression if they are still receiving clinical benefit, as judged by the Investigator, and in the absence of any other discontinuation criteria.**

### Section 4.4: modified

Removal of the patient registry after national reimbursement. This means that the data collection for ASTRIS stops at the last patient last visit.

### Section 5 modified

Disease characteristics / Disease assessment: Addition of the collection of information at entry and at progression, about **leptomeningeal /brain metastases** in the CRF. This was missed from the beginning.

Survival status: ~~For patients entering in the registry, the date of death in the follow-up period will be used to evaluate OS.~~

### Section 6.7 Study governance and oversight added

**An Executive Steering Committee will be set up. It will involve 7 experts with the relevant knowledge and experience required for the study. This Executive Committee will have the executive oversight and supervision of the study. It will also be involved in the publication strategy of the study.**

### Section 7.2 modified

Publication or presentation of data subsets from individual institutions, regions or countries participating in this global multicentre studies may ~~must not~~ precede the primary manuscript with the approval of the AZ global study team. ~~, and when developed must always reference the primary publication of the entire study.~~ **The AZ global study team will determine if in certain instances publication of institution, regional or country-specific data by the participating country may precede the primary global publication.**

Following a recommendation from the Executive Steering Committee.

### Section 9.2 modified

Addition of the definition for **Response Rate (RR): RR is defined as the percentage of patients with a best response of ‘responding’ by investigator assessment as recorded in the CRF.**

Addition of **Time to treatment discontinuation (TTD):**

**TTD is defined as the time from the date of first dose of AZD9291 in this study until the**

**date of AZD9291 discontinuation for any reason including disease progression, treatment toxicity, death or other reason as recorded in CRF. Subjects who are still on treatment at the time of analysis will be censored at the date of last dose received.**

Following a recommendation from the Executive Steering Committee.

**Section 9.4.2** modified

**PFS and TTD** will be summarized similarly to OS using KM estimates of the median times to progression or death, treatment discontinuation and quartiles together with their 95% CIs. KM estimates of the **PFS or TTD** rate at appropriate time points (to be defined in SAP) will be presented as well. A plot of the KM **PFS and TTD** curve will be produced.

**The response rate will be summarised together with the 95% CI.**

**Section 9.4.4 Interim analysis** added

**Interim analysis of the global data will take place annually for the first three years (i.e. at approximately 12, 24 and 36 months from the start of recruitment) to provide annual updates of key study measures as specified in the SAP. Regional and country level analysis may also be performed at these time points if deemed appropriate.**

**The final analysis will take place approximately 5 years after the start of recruitment, depending on the date of actual global study closure.**

**Section 9.5** modified

The table illustrating the precision for OS was adapted with a revised patient's distribution and increased study length based on the Collett formula.

**Section 11.5** modified

In case of amendment to a protocol, only a revised protocol is prepared to be approved by the relevant IRB/EC. To comply with change in AstraZeneca SOP.

**Version 1.0, 30 June 2015**

**Is applicable to all participating countries. Refer to the Protocol Amendment 1 for details.**

Changes to the protocol are summarised below.

**Section of protocol synopsis - Study site(s) and number of patients planned-** was modified to include America and Asia.

**Section of protocol synopsis- Duration of IP administration and Section 10.2.4 Timetable and End of Study** were modified to add a clause about study termination in each country.

**Section of protocol synopsis - Statistical methods** was amended to provide a more detailed and robust description of the statistical evaluations.

**Section of protocol affected: Study Plan (Table 4)** was amended to provide a more detailed study plan in line with the CRF as well as more details about the enrolment process and clarification about the T790M testing and what will happen to the samples if a central laboratory is used.

**Section of protocol affected: 4.2 Restrictions** was amended to provide clarity in male patients contraception.

**Section 4.3 Discontinuation from study:** a new paragraph **‘4.3.1 Procedures for discontinuation of a subject from study treatment’** was added to provide details about procedures for discontinuation from study treatment.

**Section 4.4 Patient Withdrawal or Study Termination** was amended to provide details about what will happen in case of study withdrawal and for the follow-up of overall survival.

**Section 5. Study Measures** was amended to provide a more detailed list of study measures collection in line with the CRF.

**Section 6. Safety reporting and medical management** was amended to provide clarity about SAE reporting timeframes and add instructions about follow-up of unresolved adverse events.

**Section 6.6.2 QTc Prolongation (using Fredericia’s formula –QTcF–)** was amended to be aligned with the AZD9291 Core Data Sheet:

**Section 8.1 Identity and dose of investigational product – AZD9291** was modified to be aligned with the AZD9291 Core Data Sheet

**Section 9 Statistical Analyses** was rewritten to provide a more robust description of the statistical evaluations and sample size determination.

## LIST OF ABBREVIATIONS

Abbreviation or special term	Explanation
AE	Adverse Event
AESI	Adverse Event of Special Interest
BCR	Best Clinical Response
CI	Confidence Interval
CNS	Central Nervous System
CRF	Case Report Form
CT	Computer Tomography
CTCAE	National Cancer Institute Common Terminology Criteria for AEs
ECG	Electocardiogram
EGFR	Epidermal Growth Factor Receptor
FAS	Full Analysis Set
FDA	Food and Drug Administration
FDG-PET	Fluorodeoxyglucose -Positron Emission Tomography
ICH-GCP	International Conference on Harmonisation - Good Clinical Practice
ILD	Interstitial Lung Disease
IVRS/IWRS	Interactive Voice Response System/ Interactive Web Response System
KM	Kaplan-Meier
MedDRA	Medical Dictionary for Regulatory Activities
MRI	Magnetic Resonance Imaging
NSCLC	Non-Small Cell Lung Cancer
ORR	Objective Response Rate
OS	Overall Survival
PT	Preferred Term
PMDA	Pharmaceuticals and Medical Devices Agency
PFS	Progression Free Survival
QTc	The QT interval corrected for heart rate

---

Abbreviation or special term	Explanation
QTcF	QT interval corrected per Fredericia's formula
RECIST	Response Evaluation Criteria In Solid Tumors
RR	Response Rate
SAE	Serious Adverse Event
SAP	Statistical Analysis Plan
SAS®	A commercially available integrated system of software products, commonly used for reporting and analysis of Clinical Studies
SOC	System Organ Class
TKI	Tyrosine Kinase Inhibitor
TTD	Time to Treatment Discontinuation
WHO	World Health Organization

## 1 STUDY DETAILS

### 1.1 Study Objectives

The primary objective of this study is to assess the efficacy and safety of single agent AZD9291 in a real world setting in adult patients with advanced or metastatic, epidermal growth factor receptor (EGFR) T790M mutation-positive Non-Small Cell Lung Cancer (NSCLC), who have received prior EGFR-tyrosine kinase inhibitor (TKI) therapy.

### 1.2 Study Design

This is an open-label, single-arm, multinational, multicenter, real world treatment study. The target patient population is adult patients (fulfilling the definition of “age of majority” per local regulations) with locally advanced (stage IIIB) or metastatic (stage IV) NSCLC with a confirmed T790M mutation, who have received prior EGFR-TKI therapy.

### 1.3 Number of Patients

Overall Survival (OS) is the primary efficacy endpoint for this study. Median OS is assumed to be approximately 21-25 months in patients with advanced or metastatic EGFR T790M mutation-positive NSCLC who have received prior therapy with an EGFR-TKI and are receiving treatment with AZD9291. While the sample size is not known a priori illustrations of the precision with which OS could be calculated from this real world study are given in the table below. These illustrations assume a study length of 58 months with non-uniform accrual over 40 months and that OS is exponentially distributed.

N	21 Months OS		23 Months OS		25 Months OS	
	n events	95% CI median OS*	n events	95% CI median OS*	n events	95% CI median OS*
500	313	18.8-23.5	297	20.5-25.8	283	22.3-28.1
1000	627	19.4-22.7	595	21.2-24.9	566	23.0-27.1
1500	941	19.7-22.4	893	21.5-24.6	800	23.3-26.8
2000	1255	19.9-22.2	1191	21.7-24.3	1133	23.6-26.5
3000	1883	20.1-22.0	1787	22.0-24.1	1700	23.8-26.2
3500	2197	20.1-21.9	2085	22.0-24.0	1983	23.9-26.1

\*95% CI is based on the formula in Collet 1994 (Collett, 1994)

Therefore if 3500 patients enter the study globally and the median OS is 25 months the 95% confidence interval (CI) around this survival figure would be approximately 23.9-26.1 months, assuming 1983 OS events (57% maturity). For Europe, assuming recruitment of 1000 patients and 566 OS events, the equivalent 95% CI would be approximately 23.0-27.1 months.

## 2 ANALYSIS SETS

As this is a real world study investigating the efficacy and safety of AZD9291, all analyses will be performed on the full analysis set, unless otherwise indicated.

### 2.1 Definition of analysis set

#### Full Analysis Set (FAS)

The full analysis set will include all patients who received at least one dose of study treatment (i.e. with at least one start date in the Administration of the Study drug page in the CRF).

### 2.2 Violations and deviations

All major deviations related to the study inclusion or exclusion criteria and study conduct will be listed and summarised.

The following general categories will be considered major deviations. This list is not exhaustive and additional important deviations may be added prior to database lock.

- Informed consent procedure deviation Missing subject' signature from the informed consent document or other International Conference on Harmonisation - Good Clinical Practice (ICH-GCP) violation related to informed consent; laboratory or urinalysis samples or electrocardiogram (ECG) date before informed consent date and not performed per standard of care but on study purpose)
- Eligibility criteria deviation (any inclusion criteria not met or exclusion criteria met)
- Prohibited medication deviation (e.g., patients received other anticancer agents, investigational agents, or radiotherapy while on study treatment)
- Procedures/Tests deviation (ECG or ophthalmologic assessment or WHO performance status not performed at screening visit)
- Investigational product administration deviation (Overdose; Screening assessment date not within 28 days before start of treatment; Incorrect procedure for T790M obtainment; New or worsening pulmonary symptoms or radiological abnormality suggestive of Interstitial Lung Disease (ILD) observed, but study treatment not interrupted; Patient experiencing grade 3 QT interval corrected per Fredericia's formula (QTcF) with QTcF prolongation, but study treatment not interrupted)
- Withdrawal criteria deviation (Any withdrawal criteria met)
- Adverse Event (AE) / Serious Adverse Event (SAE) deviation (SAE / AE of special interest not reported in CRF within 24 hours of become aware)

The categorization of these as major deviations is not automatic and will depend on the duration and the perceived effect on efficacy.

All protocol deviations are defined in Protocol Deviation Specification document version 5.0 where a category Programmable / Observable is assigned to each deviation. Programmable deviations are programmed while Observable are checked manually during monitoring visits. Programmable deviations are then imported, and observable deviations are entered in a Protocol Deviation Tool according to classification defined in the Protocol Deviation

Specification. All deviations are then reviewed and classified on a monthly basis as Major/Minor.

A review of major protocol deviations will be performed during the data review meeting and prior to database lock, together with the lead medic, statistician and data manager.

The major protocol deviations or violations assessed to have potential impact the efficacy and safety analyses will be summarised with the pre-specified categories (refer to Protocol Deviation Specification document version 5.0).

If the number and severity of major protocol deviations which are considered to have the potential to impact the primary analysis during this review before Database lock, is considered important, sensitivity analyses may be performed. This will be decided during the data review meeting and before the database lock.

### **3 PRIMARY AND SECONDARY VARIABLES**

#### **3.1 Efficacy**

In this real world study tumor evaluation is per institutional standard of care, recommended to be at approximately 12 week intervals. The date of tumor assessment, method of evaluation (CT, MRI, X-ray, Ultrasound, Bone Scan, FDG-PET, Clinical examination) and the investigators opinion of the patient status (responding, stable disease, progressing) is captured in the tumor evaluation CRF.

##### **3.1.1 Overall Survival (OS)**

The follow-up for the patients' survival status is to be performed every 6 weeks ( $\pm 1$  week) relative to the date of enrolment until end of study.

Overall survival is defined as the time from the date of first dose of AZD9291 in this study until the date of death due to any cause (i.e. date of death or censoring – date of first dose of AZD9291 in this study + 1). Any patient alive at study discontinuation will be censored at the study discontinuation date.

##### **3.1.2 Progression Free Survival (PFS)**

Progression Free Survival is defined as the time from the date of first dose of AZD9291 in this study until the date the disease is considered by the investigator to be progressing (as recorded in the tumour evaluation CRF and irrespective of the method of evaluation) or the date of death (by any cause in the absence of progression) regardless of whether the patient withdraws from therapy or receives another anti-cancer therapy prior to progression (i.e. date of disease progression or death – date of first dose of AZD9291 in this study + 1). Patients who have not progressed or died at study discontinuation will be censored at the time of the latest date of disease assessment. Patients with no post baseline disease assessment will be censored at Day 1.

The PFS time will always be derived based on the date of tumour assessment or death and not visit dates.

### 3.1.3 Time to Treatment Discontinuation or Death (TTD)

As a supportive summary to PFS, time to treatment discontinuation or death will be assessed and is defined as the time from the date of the first dose of AZD9291 in the study until the date of AZD9291 discontinuation (as recorded on the discontinuation of study drug CRF) or death, regardless of the reason for discontinuation (disease progression, treatment toxicity or other reason as recorded in the CRF). This will be calculated as: date of AZD9291 discontinuation or death – date of first dose of AZD9291 + 1. Patients who transitioned to commercial supply will be censored at the date of discontinuation of study treatment (date of their last dose of study treatment).

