### **4.3 Discontinuation from study treatment**

Patients may be discontinued from AZD9291 treatment in the following situations:

- The investigator thinks that it is in the patient's best interest to stop therapy (i.e. disease progression or patient is no longer receiving clinical benefit)
- Patient decision: the patient is at any time free to discontinue treatment, without prejudice to further treatment.
- Confirmed diagnosis of ILD
- Ulcerative ocular events
- QTc interval prolongation with signs/symptoms of serious arrhythmia
- Other manifestation of unacceptable toxicity
- Pregnancy
- Patient incorrectly enrolled or treated on the study
- Patient starts receiving additional anti-cancer therapy

- Lost to follow up (unsuccessful contact with patient despite every effort made by investigator)
- Termination of the study (see Sections 4.4 and 10.2.4)

All unused investigational product (IP) must be returned by the patient or representative (e.g. caregiver, family member).

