### **10.2.4 Timetable and End of Study**

The study is expected to start in Q3 2015 and to end by Q2 2020.

The study will be closed in each participating country as soon as possible following national reimbursement of AZD9291 in that country (up to a max of 90 days post reimbursement). Enrolment will be closed within 6 months after market license approval in that country or at national reimbursement, whichever is sooner.

Patients withdrawing from the treatment prior to national reimbursement will be followed up as part of this study.

At national reimbursement, patients still on treatment will be transitioned to commercial supply as long as patient is benefitting from treatment as per investigator assessment and in accordance with national regulations in the countries where the study is conducted. Once the study is closed no further data will be collected.

In the event that national reimbursement should not be granted following a reasonable time after market license approval in the country, the study will be closed in a maximum period of 18 months after the last patient is enrolled in that country. Contingencies will be made locally to ensure continued drug supply for patients who are still deriving benefit from AZD9291 at that time.

The end of the study is defined as ‘the last visit of the last subject undergoing the study’.

AstraZeneca may also terminate the entire study prematurely if concerns for safety arise within this study or in any other study with AZD9291.

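### SAP 3.1.3 does not say how TTD treats a patient still on drug when a country closes without reimbursement; read literally, closure counts as an event

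*SAP*

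**What the plan says.** SAP 3.1.3 defines the TTD event as AZD9291 discontinuation, dated from the study-drug discontinuation CRF, or death, "regardless of the reason for discontinuation (disease progression, treatment toxicity or other reason as recorded in the CRF". It gives one censoring rule: "Patients who transitioned to commercial supply will be censored at the date of discontinuation of study treatment". SAP 4.2.7 and the visible text of the SAP addendum add no other TTD rule.

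The neighbouring endpoints have a general rule for patients who leave the study event-free. For OS (SAP 3.1.1): "Any patient alive at study discontinuation will be censored at the study discontinuation date". For PFS (SAP 3.1.2): "Patients who have not progressed or died at study discontinuation will be censored", at the latest disease assessment.

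Protocol 4.3 includes among the situations for stopping AZD9291 "Termination of the study (see Sections 4.4 and 10.2.4". Protocol 10.2.4 describes two kinds of administrative closure. After national reimbursement, patients still benefiting move to commercial supply. If reimbursement is not granted within a reasonable time, "the study will be closed in a maximum period of 18 months after the last patient is enrolled in that country", and "Contingencies will be made locally to ensure continued drug supply for patients who are still deriving benefit from AZD9291 at that time".

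Protocol 9.2 has its own TTD rule: patients still on treatment at the analysis are censored at their last dose. SAP section 6 (changes from protocol) is marked not applicable.

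**The concern.** The SAP's exception for commercial supply shows that its authors did not want an administrative switch of supply to count as stopping treatment. The exception names only one of the two closure routes in the protocol. A patient who is benefiting when a country closes without reimbursement ends study drug, may have a discontinuation form giving study termination as the reason, and continues on locally arranged supply. A programmer who follows SAP 3.1.3 as written would code an event.

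TTD rates are planned out to 36 months (SAP 4.2.7, fixed time points), and TTD is also reported by country of enrolment (SAP 4.2.7, subgroups). Closure counted as an event would make on-treatment rates too low, and countries could then differ because of how they closed rather than how long patients stayed on drug.

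**Working it through.** **Step 1: is the case covered?**

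| Situation when study drug ends | Rule in SAP 3.1.3 | Rule elsewhere |
|---|---|---|
| Progression, toxicity, other reason, death | Event | Protocol 9.2: event |
| Move to commercial supply | Censored | – |
| Still on study drug at the analysis | Not stated | Protocol 9.2: censored at last dose |
| Country closes without reimbursement, local contingency supply | Event if a discontinuation is recorded and not coded as commercial | Protocol 9.2: unclear, since study drug has ended |

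The last row is the gap.

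**Step 2: inputs for an illustration.** The documents state no TTD figure, so there is none to reproduce. Assumed: exponential TTD with a median of 12 months (range 9.6 to 15; 9.6 is the protocol's preliminary median PFS, used only as a low value) and a share *p* of patients in countries closed without reimbursement (5, 10 or 20%).

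Follow-up is calibrated to the OS table in SAP 1.3, which uses 58 months of study and non-uniform accrual over 40 months. With entry time 40·√U (U uniform on 0–1) and exponential OS, expected events per 1000 at medians 21, 23 and 25 months are 628, 596 and 567, against 627, 595 and 566 in the table. Follow-up is then 58 − 40·√U, from 18 to 58 months, and the fraction followed beyond *t* is G(t) = ((58 − t)/40)². This gives 0.7225, 0.490 and 0.3025 at 24, 30 and 36 months.

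**Step 3: closure at the full 18 months, all countries with the same follow-up pattern.** The correct rate is 2^(−t/median). With closure counted as an event it is 2^(−t/median) × G(t)^p. For example, at 36 months with p = 0.10: 0.125 × 0.3025^0.10 = 0.125 × 0.887 = 0.111.

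| Median 12 | 24 mo | 30 mo | 36 mo | False events of 3500 |
|---|---|---|---|---|
| Correct | 25.0% | 17.7% | 12.5% | 0 |
| p = 5% | 24.6% | 17.1% | 11.8% | about 33 |
| p = 10% | 24.2% | 16.5% | 11.1% | about 65 |
| p = 20% | 23.4% | 15.3% | 9.8% | about 131 |

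False events are 3500 × p × the mean of 2^(−follow-up/12). At p = 10% the 36-month rate is 6.6% instead of 7.4% for median 9.6, and 16.8% instead of 18.9% for median 15. Rates through 18 months, and a median below 18 months, do not move.

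**Step 4: shorter entry windows in the closing countries.** Let entry there be uniform over W = 6, 12 or 24 months (assumed), with closure 18 months after the last entry. The added hazard is p·g_N(t)/[p·G_N(t) + (1 − p)·G(t)], where G_N and g_N are the survival function and density of follow-up in those countries. For median 12, the 24/30/36-month rates are 22.1–24.3 / 15.2–16.5 / 10.8–11.0% at p = 10% and 19.3–23.6 / 12.9–15.3 / 9.1–9.6% at p = 20%.

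**Step 5: earlier closure.** Eighteen months is a maximum. Take p = 10%, W = 12 and closure 6 months after the last entry, so follow-up in those countries runs from 6 to 18 months while the others are all followed to at least 18. For t between 6 and 18 the rate is 2^(−t/12) × [0.9 + 0.1 × (18 − t)/12]. At 12 months this is 0.500 × 0.95 = 47.5% instead of 50.0%. The median is about 11.2 months instead of 12.

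**The case against.** The strongest reply is that the plan already has the rule. Protocol 9.2 censors patients still on treatment, and SAP section 6 declares no departure from the protocol. Patients on contingency supply have arguably not discontinued AZD9291 at all. The protocol synopsis mentions conversion to commercial drug directly after the contingency sentence, so sites may have coded these patients as commercial transitions. The CRF is not in the documents, no passage shows that any country closed this way, and much of SAP section 5 is redacted.

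Much of this stands. A reader might infer that the plan has no protection for these patients, or that TTD will be biased; the documents support neither. What remains is narrower. SAP 3.1.3 dates the event from the study-drug discontinuation form, a patient with such a form is not clearly still on treatment, and no passage equates contingency supply with commercial supply. The outcome would rest on undocumented coding.

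The illustration is also open to challenge. The 18–58 month follow-up comes from a global OS precision example. Countries with reimbursement close within 90 days of it, so follow-up there could be well under 18 months. The figures show direction and rough scale only.

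**Conclusion.** The gap in SAP 3.1.3 is real, and the point is minor. If closure is counted as an event, the error can only lower the on-treatment rates. It is confined to rates after 18 months if closure comes at the full 18 months after the last enrolment; sooner closure also lowers earlier rates and the median. A reader who looks only at the 18-month limit might infer that the median is always safe, but the protocol sets that limit as a maximum.

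The size is not known from the documents. The median, the share of patients, the entry windows and the earlier-closure example are all assumptions. The effect is zero if no such closure occurs with patients on drug, or if all such patients are coded as commercial transitions. No figure is offered for the comparison between countries, because country accrual windows are not given.

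It would be wrong to infer that the main efficacy result is at risk. OS and PFS have their own censoring rules and are not touched, protocol 9.4 plans no statistical tests, and the SAP gives TTD a secondary role: "As a supportive summary to PFS, time to treatment discontinuation or death will be assessed".

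**What to change.** In SAP 3.1.3:

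- Restate the protocol 9.2 rule that patients still on treatment at the analysis are censored at their last dose.
- Censor at the last study dose any patient whose only recorded reason for ending study treatment is administrative study or country closure, including a move to commercial, contingency or other supply.
- Keep all other discontinuations and deaths as events. This includes discontinuation because the sponsor terminates the study for safety or undue risk (protocol 4.4 and 10.2.4). Censoring every study closure would wrongly remove those.
- Report the number of patients censored for closure.

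The cost is two or three sentences and one derivation keyed on the recorded discontinuation reason, with no data needed after closure. Before database lock, confirm that the CRF reason list can separate administrative closure from termination for safety. If no patient is affected, the results do not change.
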